7.2 Software to be Used for Statistical Analysis

Windows SAS 9.3 will be used for statistical analysis.

Microsoft Excel 2010 will be used to output analytical data sheets but not for the calculation of statistics.

7.3 Statistical Methods

Categorical data including categories of continuous data will be presented using the number and percentage of subjects in each category. Missing values will normally be excluded from the calculation of frequencies. Data in the "Unknown" category will be included in the summarization of patient characteristics but excluded from that of efficacy variables because they are equivalent in nature to missing values.

Improvement rates will be calculated as the percentage of subjects with an improvement of at least one category among those with assessments other than "Unknown" available before and after treatment.

Continuous data will be presented using the following summary statistics: number of subjects, mean, standard deviation, median, minimum, and maximum.

Summary statistics will be reported to one more digit than the significant figures for mean, standard deviation, and median, and to the same number of digits as the significant figures for minimum and maximum.

The following procedures will be used for statistical testing and interval estimation:

1) Testing for comparing pre- and post-treatment values and scores

The UNIVARIATE procedure will be used to compare pairs of pre- and post-treatment values by the sign test, Wilcoxon signed-rank test, etc. In the comparison of scores, values equivalent to "Unknown" will be excluded before testing.

2) Calculation of confidence intervals for incidence rates (improvement rates)

The EXACT BINOMIAL option of the FREQ procedure will be used to calculate exact confidence intervals based on binomial distribution.

8 Statistical Analysis Variables

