- For a chocolate cyst of the ovary newly confirmed during the treatment period, whether it is a cyst that has not been accidentally measured before treatment initiation or a new cyst will be inputted in the column for comments.
- For a chocolate cyst of the ovary that becomes difficult to identify during the treatment period, such a fact and its number will be entered in the column for comments.

(v) Severity of dysmenorrhea (dysmenorrhea severity score)

- The severity of dysmenorrhea will be assessed in accordance with Table 2, and a score will be entered. A dysmenorrhea score²⁾ will be calculated using a total of the recorded score and a score for the use of analgesics.

(vi) Use of analgesics (including over-the-counter drugs) for the treatment of dysmenorrhea (score for the use of analgesics)

- The use of analgesics will be assessed in accordance with Table 3, and a score will be entered. A dysmenorrhea score will be calculated using a total of the recorded score and a dysmenorrhea severity score.

(vii) Visual analogue scale (VAS) for dysmenorrhea

- The VAS for dysmenorrhea will be assessed in accordance with Table 4. A length (cm) from the left end of the line (0) will be measured. Measured values (cm) will be rounded off to one decimal place and inputted.

[figure not shown]
Table 2 Severity of dysmenorrhea

Severity of dysmenorrhea	Contents	Score
None	None	0
Mild	Rarely interfering with work (study and house work)	1
Moderate	Interfering with work (study and house work) requiring lying down to rest	2
Severe	Being confined to bed for ≥ 1 day, being unable to work (study and house work)	3

Table 3 Use of analgesics

Use of analgesics	Contents	Score
None	None	0
Mild	An analgesic was used for a day during the last (or current) menstruation period.	1
Moderate	An analgesic was used for 2 days during the last (or current) menstruation period.	2
Severe	An analgesic was used for ≥ 3 days during the last (or current) menstruation period.	3

Table 4 VAS for dysmenorrhea

(viii) Concomitant medications/therapies (If “yes,” the name of a drug, daily dose, route of administration, reason for administration, start date of administration, end date of administration, name of concomitant therapy, reason for implementing concomitant therapy, start date of concomitant therapy, and end date of concomitant therapy will be inputted.)

(ix) Date of withdrawal/dropout and its reason

(3) Laboratory tests

(i) Serum CA125

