**Post Marketing Observational Study
Statistical and Analytical Plans**

(DUPKST16002)

**A SURVEY ON EFFICACY AND SAFETY IN PATIENTS
WITH ENDOMETRIOSIS**

Ver. 1.0

Changes in the Statistical Analysis Plan

Version 1.0 of the statistical analysis plan was finalized on September 15, 2017. No revisions were made to the plan thereafter.

Table of contents

1	Introduction	4
2	Outline of the Study.....	4
3	List Of Abbreviations And Definition Of Terms.....	4
4	Organization for Statistical Analysis Activities	4
5	Study Design.....	5
5.1	Study Schedule	5
5.2	Outcome measures	6
5.3	Determination of Sample Size.....	6
6	Handling of Data	6
6.1	Analysis Set.....	6
6.2	Handling of Data by Period.....	6
6.3	Handling of Data to Derive Variables.....	7
6.4	Handling of Adverse Event Data.....	7
7	Matters concerning statistical analysis	7
7.1	Level of Significance for Statistical Testing and Confidence Level for Interval Estimation.....	7
7.2	Software to be Used for Statistical Analysis	7
7.3	Statistical Methods	7
8	Statistical Analysis Variables	8
8.1	Disposition of Subjects	8
8.2	Patient Characteristics	8
8.3	Efficacy Variables.....	9
8.3.1	Study Primary Variables	9
8.3.2	Study Secondary Variables	9
8.4	Safety Variables	10
8.4.1	Adverse Events	10

1 Introduction

This document provides details of the statistical analysis plan for the “Post Marketing Observational Study of Duphaston Tablets 5 mg - a Survey on Efficacy and Safety in Patients with Endometriosis” (hereinafter referred to as the “study”). The purpose of the statistical analysis plan is to ensure that data are analyzed properly and efficiently as planned.

2 Outline of the Study

Duphaston tablets have been available for the treatment of endometriosis in Japan since 1965. This study is designed to collect efficacy and safety data in patients with endometriosis to obtain information for the effective and safe use of Duphaston tablets.

Clinical Supply	Duphaston® 5 mg Tablets
Title (Protocol Number)	Post Marketing Observational Study A SURVEY ON EFFICACY AND SAFETY IN PATIENTS WITH ENDOMETRIOSIS (DUPKST16002)
Study Design	Prospective, non-intervention, non-blind, non-control observational study
Observation period	4 cycles
Planned sample size	65 subjects

3 List Of Abbreviations And Definition Of Terms

Term/abbreviation	Definition
The summary statistics	Number of subjects, mean, standard deviation, minimum, median, and maximum

4 Organization for Statistical Analysis Activities

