6.1 Analysis Set

The analysis set will consist of all subjects who satisfy inclusion and exclusion criteria and are enrolled in this survey.

The efficacy evaluation will be summarized in the “efficacy analysis set,” which consists of all subjects who receive Duphaston and for whom any of the efficacy variables are observed. The evaluation will also be summarized in the “study completers,” which consists of subjects who complete the treatment without discontinuation.

The safety evaluation will be summarized in the “safety analysis set,” which consists of all subjects who receive the drug.

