6.2 Handling of Data by Period

Since the observation period will be set based not on the number of days from the start date of administration but on the menstruation cycle, and the observation data in each menstrual cycle will be obtained from investigation of status per cycle without identifying the first day of menstruation as a base point, the cycles entered in the EDC system will be used as they are and each item will be summarized according to the applicable observation schedule, namely before the start of treatment (cycle -1), at the start of treatment (cycle 1), cycle 2, cycle 3, cycle 4 and at the completion of the observation period (cycle 5). The last observation of the actual evaluations after cycle 1 including those at discontinuation (except for “unknown”) will be summarized as “at last observation.”

Since the recommended regimen of this survey is to start the dosage on the fifth day of each menstrual cycle, the administration can be started during menstruation of cycle 1.

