6.3 Handling of Data to Derive Variables

(1) Age

If the birth date and the start date of administration are available, the age at the start date of administration will be calculated. If these dates are not available, the age entered in the EDC system will be used.

(2) Volume of ovarian chocolate cyst

The value used will be automatically calculated by the EDC system with the following conversion formula using the major axis (D1 [cm]) and minor axis (D2 [cm]) of ovarian chocolate cyst.

$$\text{Volume [cm}^3\text{]} = \{(D1 + D2) \times 1/2\}^3 \times 0.52$$

(3) Dysmenorrhea score

The dysmenorrhea score used will be a total of a dysmenorrhea severity score and a score for the use of analgesics and automatically calculated by the EDC system. If either of the scores is unknown, the dysmenorrhea score will be handled as unknown.

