8.3.2 Study Secondary Variables

(1) Change in the severity of dysmenorrhea

In each analysis set, namely “efficacy analysis set” and “study completers,” the frequency of categories compared to the value before treatment will be calculated by cross tabulation, and the improvement rate and its 95% confidence interval (CI) will be calculated, at each observation point and last observation.

(2) Change in the use of analgesics

In each analysis set, namely “efficacy analysis set” and “study completers,” the frequency of categories compared to the value before treatment will be calculated by cross tabulation, and the improvement rate and its 95% CI will be calculated, at each observation point and last observation.

(3) Change in the dysmenorrhea score

In each analysis set, namely “efficacy analysis set” and “study completers,” the frequency compared to baseline will be calculated by cross tabulation, and the improvement rate and its 95% CI will be calculated, at each observation point and last observation. The score value and difference from the value before treatment will be calculated at the same points using the summary statistics, and the Wilcoxon signed-rank test will be performed.

(4) Change in the severity of dysmenorrhea pain (VAS)

In each analysis set, namely “efficacy analysis set” and “study completers,” the difference from the value before treatment and change rate will be calculated using the summary statistics at each observation point and last observation, and the Wilcoxon signed-rank test will be performed for the difference and change rate.

(5) Change in serum CA125

Separately in the “efficacy analysis set” and “study completers,” the values before treatment initiation and at last observation will be compared, the value, difference from the value before treatment and change rate will be calculated using the summary statistics, and the Wilcoxon signed-rank test will be performed for the difference and change rate.

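### The SAP 7.3 improvement rates count every subject scored 0 before treatment as not improved, and no supplementary rate among subjects able to improve is planned

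*SAP*

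**What the plan says.** - **Definition.** SAP 7.3: "Improvement rates will be calculated as the percentage of subjects with an improvement of at least one category among those with assessments" other than Unknown before and after treatment. Unknown values are the only ones taken out; a pre-treatment score of 0 is not. Intervals are exact binomial.
- **Use.** SAP 8.3.2 (1)-(3) reports the rate with a 95% CI for dysmenorrhea severity, analgesic use and the dysmenorrhea score, at each observation point and at last observation, in the efficacy analysis set and in study completers. For severity and analgesic use, "the frequency of categories compared to the value before treatment will be calculated by cross tabulation". For the score a cross tabulation is also planned, and in addition "The score value and difference from the value before treatment will be calculated at the same points using the summary statistics", with a Wilcoxon signed-rank test.
- **Scales.** Protocol section 7, Tables 2 and 3, run from 0 (None) to 3. Table 3 counts days of use only: a score of 1 means "An analgesic was used for a day during the last (or current) menstruation period". The dysmenorrhea score is the sum of the two, so it runs from 0 to 6. SAP 6.3 (3) adds: "If either of the scores is unknown, the dysmenorrhea score will be handled as unknown".
- **Who is included.** Protocol 4.1.1 selects on age, cyst size and menstrual cycle. Nothing listed in 4.1.2 removes women without pain or analgesic use. Under SAP 6.1 the efficacy analysis set "consists of all subjects who receive Duphaston and for whom any of the efficacy variables are observed".
- **Testing.** The opening sentence of SAP 8.3 says that every efficacy variable will be tested before against after treatment. 8.3.2 (1) and (2) name no test.

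**The concern.** Zero is the lowest value on each scale. A subject at 0 before treatment can only stay there or worsen, yet she is in the denominator and is counted as not improved. The planned rate therefore combines two things: how many subjects had the symptom (or used an analgesic) at baseline, and how often those subjects improved.

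The survey's stated aim is to inform effective use of the drug in endometriosis. A natural question is how often women with dysmenorrhea improved, and for this the plan gives no estimate with an interval. If many subjects start at 0, a reader who takes the planned rate as that answer will understate it.

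The group able to improve depends on the scale. A woman with pain who takes no analgesic is at 0 in Table 3 but not in Table 2. For analgesic use, the relevant group is women who had used an analgesic, not women with pain.

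**Working it through.** **Plan's own figure.** The documents give no figure for the improvement rates. The nearest stated numbers are 58 and 65, for the primary sign test on cyst volume (SAP 5.3). They reproduce if 80% power is assumed, since power is not stated. With 0.70 against 0.50 at two-sided 5%, the continuity-corrected normal approximation gives 51.5, so 52 subjects with a change; 52 / 0.9 = 57.8, so 58; 58 / 0.9 = 64.4, so 65. The point does not depend on this. I use 58 below only as an illustrative number assessed.

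**Inputs**
- Denominator and numerator: SAP 7.3.
- Floor of 0: Protocol Tables 2 and 3, and the sum in SAP 6.3 (3).
- f, the share of assessed subjects at 0 before treatment: not given; assumed 0 to 40%.
- r, the improvement rate among the others: not given; assumed 40 to 70%, with 60% as the central value.

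**Formulas.** Of N assessed, fN are at 0 and contribute no improvements; (1 - f)N can improve, and a share r of them do.
- Planned rate = (1 - f) x N x r / N = (1 - f) x r.
- Ceiling (r = 1) = 1 - f.
- Gap below r = r - (1 - f) x r = f x r, whatever N is.

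| f | ceiling | planned rate at r = 60% | gap at r = 60% | gap over r = 40-70% |
|---|---|---|---|---|
| 0 | 100% | 60% | 0 | 0 |
| 5% | 95% | 57% | 3 points | 2.0-3.5 points |
| 20% | 80% | 48% | 12 points | 8-14 points |
| 40% | 60% | 36% | 24 points | 16-28 points |

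**Whole subjects, 58 assessed, r about 60%, Clopper-Pearson 95% intervals**
- f about 20%: 12 at 0, 46 able to improve, 28 improve. Planned: 28/58 = 48.3% (35.0-61.8). Among those able to improve: 28/46 = 60.9% (45.4-74.9). Gap 12.6 points.
- f about 40%: 23 at 0, 35 able to improve, 21 improve. Planned: 21/58 = 36.2% (24.0-49.9). Among those able to improve: 21/35 = 60.0% (42.1-76.1). Gap 23.8 points; interval widths 25.9 and 34.0 points.

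**f by scale.** The total score is 0 only when both components are 0. Among subjects with both known, f for the total therefore cannot exceed f for either component, and eligibility has to be set scale by scale.

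**The case against.** The strongest reply is that nothing is wrong. The denominator is stated openly, the rate and interval are valid for all assessed subjects, and the planned cross tabulations show the number at 0, the number improved and the number who worsened from 0. Anyone can derive the second rate and its interval from those counts. The planned rate is also the more cautious one: removing subjects at 0 can never lower it. All of this stands, so this is a reporting gap and not an error. What remains is that the reader must do the derivation, and that a rate fixed in advance avoids a choice of denominator after the results are known.

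Three stronger readings are tempting, and the documents do not support them.
- *The planned rate is biased.* It is not; it answers a question about all assessed subjects.
- *Severity and analgesic use are assessed by this rate alone.* 8.3.2 (1) and (2) name only the cross tabulation and the rate, but the opening of SAP 8.3 promises a before-after test for every variable and 7.3 lists paired tests. The text leaves open which test applies to these two. A test would not supply the missing rate in any case.
- *The three rates will mislead when set against each other.* The SAP plans no comparison between scales. Nor is there reason to expect the same r on a 0-6 sum as on its 0-3 components, even with nobody at 0.

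**Conclusion.** The point holds as an inexpensive improvement to reporting. Subjects at 0 before treatment, if there are any, necessarily count as not improved; the planned rate is capped at 1 - f and lies f x r below the rate among subjects able to improve. No rate or interval for that group is planned.

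The size in this survey cannot be known from the documents, because f, r and the number assessed for dysmenorrhea are all absent. A reader might infer from the larger figures that the distortion is substantial here. That would need f near 40%, which nothing in the documents indicates; with f = 0 the two rates are the same.

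The primary cyst-volume analysis, the sample size, the Wilcoxon test on the dysmenorrhea score and the VAS analysis do not use this rate and are unaffected.

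**What to change.** Keep the planned rate as it is. After its definition in SAP 7.3 add:

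*At last observation, the improvement rate and its exact 95% CI will also be given among subjects with a pre-treatment score of at least 1 on that scale, with the number at 0 stated beside it. This rate is supplementary.*

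Refer to it in 8.3.2 (1)-(3).

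**Cost**
- No new data. 3 scales x 2 analysis sets = 6 extra rates. Reporting at all six points under SAP 6.2 (cycles 1 to 5 and last observation) would give 3 x 6 x 2 = 36, more than is needed.
- A wider interval: 34.0 against 25.9 points in the 40% illustration above.
- The rate leaves out subjects who can only stay the same or worsen. Selecting on a raised baseline in an uncontrolled survey also exposes it more to regression to the mean. For both reasons it must not replace the planned rate.
- Timing: the SAP was finalized on September 15, 2017, and it records that "No revisions were made to the plan thereafter". If the rate is added after the data were seen, it must be labelled post hoc.

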8.1 Disposition of Subjects

The following data will be presented: numbers of subjects registered, subjects with case report forms collected, subjects included in the safety analysis set, subjects excluded from the safety analysis set, subjects included in the efficacy analysis set, and subjects excluded from the efficacy analysis set.

8.2 Patient Characteristics

Patient characteristics will be summarized in the “safety analysis set,” “efficacy analysis set,” and “study completers.”

Data will be summarized according to section 7.3. The number of subjects with missing values for each item will not be shown.

Item	Categorical data: Data: Presented by category. Continuous data: The summary statistics
Age (years)	≥ 20 and < 30 years old ≥ 30 and < 40 years old ≥ 40 and < 50 years old The summary statistics
Height (cm)	The summary statistics
Weight (kg)	The summary statistics
Diagnosis	Endometriosis
Pregnancy and lactation status	No, Yes, Unknown
Menstruation status	Normal menstrual cycle, No normal menstrual cycle, Unknown
Menstrual cycle (days)	The summary statistics
Ovulation	No, Yes, Unknown
Complications	No, Yes, Unknown
Past history	No, Yes, Unknown
History of allergy	No, Yes, Unknown
History of allergy to	Drug, Other
Hepatopathy or liver disease	No, Yes, Unknown
Severity of hepatopathy or liver disease	Mild, Moderate, Severe
Heart disease	No, Yes, Unknown
Kidney disease	No, Yes, Unknown
History of drug treatment (for endometriosis)	No, Yes, Unknown
History of surgical treatment (for endometriosis)	No, Yes, Unknown

8.3 Efficacy Variables

Pre- and post-treatment values for each variable will be compared by statistical testing.

8.3.1 Study Primary Variables

(1) Change in the volume of ovarian chocolate cyst before and after treatment

For the volume calculated from the major and minor axes of ovarian chocolate cyst, the values before treatment initiation and at last observation will be compared, frequency of increase and decrease will be summarized and the sign test will be performed separately in the “efficacy analysis set” and “study completers.”

In the assessment of increase and decrease, the change rate within $\pm 15\%$ of the volume of ovarian chocolate cyst after treatment from before treatment initiation will be defined as “unchanged.”

If there are two or more cysts at a given assessment point, the total volume will be considered as the volume at that point and used for the analysis.

(2) Volume of ovarian chocolate cyst over time before and after treatment

For the volume calculated from the major and minor axes of ovarian chocolate cyst (a total volume if there are two or more cysts), the value, difference from the value before treatment and change rate will be calculated using the summary statistics at each measurement point and last observation in each analysis set, namely “efficacy analysis set” and “study completers,” and the Wilcoxon signed-rank test will be performed for the difference and change rate.

8.3.2 Study Secondary Variables

(1) Change in the severity of dysmenorrhea

In each analysis set, namely “efficacy analysis set” and “study completers,” the frequency of categories compared to the value before treatment will be calculated by cross tabulation, and the improvement rate and its 95% confidence interval (CI) will be calculated, at each observation point and last observation.

(2) Change in the use of analgesics

In each analysis set, namely “efficacy analysis set” and “study completers,” the frequency of categories compared to the value before treatment will be calculated by cross tabulation, and the improvement rate and its 95% CI will be calculated, at each observation point and last observation.

(3) Change in the dysmenorrhea score

In each analysis set, namely “efficacy analysis set” and “study completers,” the frequency compared to baseline will be calculated by cross tabulation, and the improvement rate and its 95% CI will be calculated, at each observation point and last observation. The score value and difference from the value before treatment will be calculated at the same points using the summary statistics, and the Wilcoxon signed-rank test will be performed.

(4) Change in the severity of dysmenorrhea pain (VAS)

In each analysis set, namely “efficacy analysis set” and “study completers,” the difference from the value before treatment and change rate will be calculated using the summary statistics at each observation point and last observation, and the Wilcoxon signed-rank test will be performed for the difference and change rate.

(5) Change in serum CA125

Separately in the “efficacy analysis set” and “study completers,” the values before treatment initiation and at last observation will be compared, the value, difference from the value before treatment and change rate will be calculated using the summary statistics, and the Wilcoxon signed-rank test will be performed for the difference and change rate.

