3 STUDY OBJECTIVE

This survey is intended to collect efficacy and safety data of Duphaston® Tablets in patients with endometriosis under actual condition of its use and to obtain data for effectively and safely utilizing this drug. These evaluation and test results are assumed to provide useful information for assessing the contemporary significance of treatment with Duphaston® Tablets for endometriosis, ensuring the risk management (benefit-risk ratio) in patients treated with the drug and eventually examining disease control from the viewpoint of medical economy.

4 INVESTIGATIONAL PLAN**4.1 Selection of Study Population****4.1.1 Inclusion Criteria**

The subjects of the survey will be patients with a diagnosis of “endometriosis,” an indication of Duphaston[®] Tablets, who meet the following inclusion criteria.

- (1) Women aged 20 to < 50 years
- (2) Subjects with a chocolate cyst of the ovary measuring ≥ 3 cm in diameter on transvaginal ultrasonography at patient enrollment
- (3) Subjects with a menstrual cycle of 25 to ≤ 38 days who ovulate and are confirmed to have normal menstruation at patient enrollment

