7.1 Level of Significance for Statistical Testing and Confidence Level for Interval Estimation

Unless otherwise specified, statistical testing will be performed with a two-sided level of significance of 5%, and a two-sided confidence level of 95% will be used for interval estimation. No multiplicity adjustment will be made.

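### For VAS and CA125, the signed-rank test on the change rate misses its 5% level unless variability is small (for VAS, also depending on zero baselines), and neither it nor the test on the difference is named as lead

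*SAP*

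**What the plan says.** SAP 8.3.2 (4), on VAS, and 8.3.2 (5), on CA125, both end by stating that "the Wilcoxon signed-rank test will be performed for the difference and change rate". SAP 8.3.1 (2), on cyst volume over time, carries the same clause. Nothing ranks the two tests or says how to read a split result. SAP 7.1 sets a two-sided 5% level and adds: "No multiplicity adjustment will be made".

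Two nearby places describe something simpler. For the dysmenorrhea score, SAP 8.3.2 (3) says: "The score value and difference from the value before treatment will be calculated at the same points using the summary statistics". A signed-rank test follows there, with no change rate. The general method in SAP 7.3 reads: "The UNIVARIATE procedure will be used to compare pairs of pre- and post-treatment values by the sign test, Wilcoxon signed-rank test, etc".

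On VAS, Protocol section 7 (2)(vii) says: "A length (cm) from the left end of the line (0) will be measured". A value of 0 can therefore be recorded. The inclusion criteria in Protocol 4.1.1 concern age, cyst size and a normal ovulatory cycle; they do not require dysmenorrhea. SAP 7.3 removes Unknown scores before testing and missing values from frequencies, but has no rule for an observed baseline of zero.

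**The concern.** A signed-rank test against zero holds its level only if the tested quantity is symmetric about zero when nothing has changed. The difference meets this if pre and post values are exchangeable. The change rate does not, because it cannot fall below −100% and has no upper limit.

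VAS has a second fault. A patient with baseline 0 has no change rate, so she leaves that test but stays in the test on the difference. Such a patient can only stay the same or worsen, so the loss removes only unfavourable or null changes.

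VAS and CA125 have no other planned test. If one of the paired tests is significant and the other is not, the plan gives no reading, and the reader cannot tell that one of them may not hold its stated level.

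**Working it through.** **The plan's own figure.** The only sample-size figure belongs to the sign test (SAP 5.3): 7:3 decrease to increase, 10% unchanged, 10% dropout. Power is not stated; 80% is assumed.

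- Informative pairs, 0.7 against 0.5: [(1.96 × 0.5 + 0.8416 × √0.21)/0.2]² = 46.6, and 51.5 with continuity correction, so 52.
- 52/0.9 = 57.8, so 58; 58/0.9 = 64.4, so 65.

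The plan's 58 and 65 are reproduced. The signed-rank tests have no stated figure.

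**Mechanism, no assumed SD needed.** VAS from 4 to 8 cm: difference +4, change rate (8 − 4)/4 = +100%. The exact reverse: difference −4, change rate (4 − 8)/8 = −50%. The differences tie in rank, but on the change rate the increase outranks the decrease. Under exchangeability the two patients are equally likely, so the ranks lean towards increase.

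**Simulation method.** n = 58, two-sided 5%, signed-rank test with the tie-corrected t approximation that UNIVARIATE uses above n = 20. Runs per setting were in the thousands. With 6,000 runs the simulation error near 5% is √(0.05 × 0.95/6000), about 0.3 points. All distributions are assumptions.

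**CA125.** Lognormal, median 60, between-patient log SD 0.6 to 1.0, error SD on each occasion = log-ratio SD/√2. The effect case is a true 18% fall. Ranges are over repeated simulations.

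| Log-ratio SD | Change rate rejects, no effect | The two tests disagree, no effect | Power for 18% fall, change rate v difference |
|---|---|---|---|
| 0.1 | 5.3–5.9% | about 3.6% | not computed |
| 0.2 | 6.3–6.5% | about 5% | not computed |
| 0.3 | about 8% | about 7% | 99% v 99% |
| 0.5 | 12.5–13% | 12.5–13% | 51–52% v 74–78% |
| 0.7 | about 19% | about 19% | 16–17% v 47–49% |

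- The difference test stays at 4.5–5.7% throughout.
- At SD 0.5 the change-rate rejections split into 12.7% false increase and 0.4% false decrease.
- In terms of within-patient CV, log-ratio SD = √(2 ln(1 + CV²)): CV 20%, 30% and 40% give 0.28, 0.42 and 0.54. Separate runs at these CVs gave about 8%, 11% and 14%.
- More patients do not help: at CV 30% the level is 8.9% with n = 40 and 11.0% with n = 65.

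**VAS, no effect.** Baselines of 0 are dropped from the change rate only. Two models for the zeros were tried.

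- *Floor model* (patient mean 2–5 cm, between-patient SD 2–2.5, within-patient SD 1–2, clipped to 0–10). With 1–6% zeros, false worsening is 4.5–6.2% against a nominal 2.5%. At 12% zeros the two faults cancel (2.9% improved, 2.5% worse). At 20–27% zeros, false improvement is 4.3–7.1%.
- *Zeros at random.* Total level is 9.7% with no zeros, 5.4% at 5%, 8.0% at 10%, 16.5% at 15% and 57.6% at 30%. The lean changes from worse to improved near 5% zeros.
- The difference test stays at about 4.5–5.5% in both.
- For a true fall of 0.7 cm (floor model), power on the change rate v the difference is 45% v 67%, 48% v 66% and 54% v 64% at 2%, 6% and 12% zeros.

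**The case against.** **The size is unknown.** This stands. The documents give no SD for CA125 or VAS and no share of zero baselines. At log-ratio SD 0.1 the CA125 level is close to nominal. A reader might infer that the CA125 test fails its level outright; the documents support only the conditional statement. For VAS the two models disagree on size and on where the faults cancel, so only the dependence on zeros is firm.

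**The tests are secondary, in an uncontrolled survey with no success criterion, and the valid test is already planned.** This stands as a reason for low severity. It does not remove the point, because the SAP assigns these tests a 5% level and prints two p-values of unequal standing side by side.

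**Disagreement is not all error.** Correct. At SD 0.1 the tests still disagree in about 3.6% of surveys because they weight patients differently. Only the rise above that can be put down to the skew.

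**A reader might infer that the plan is tilted towards the drug.** For CA125 the lean is to false increase, and false decrease falls below its nominal 2.5%. For VAS a lean towards improvement needs a larger share of zeros, which the documents do not give.

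**A reader might infer that the change-rate test on cyst volume should go too.** The skew is the same, but Protocol 4.1.1 admits "Subjects with a chocolate cyst of the ovary measuring ≥ 3 cm in diameter on transvaginal ultrasonography at patient enrollment", and that cut can produce regression to the mean in the difference. Applying it to the baseline scan itself (log-ratio SD 0.5, pre-selection median 3.5 cm), false decrease is 8.6% on the difference v 3.4% on the change rate. At median 6 cm, total error is 4.1% v 13.2%, the other way round. If a separate scan qualified the patient, the difference test stays near 5%. The documents settle neither the cyst sizes nor which scan qualifies.

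**Conclusion.** The point holds for VAS and CA125 and is minor. The skew of the change rate follows from its definition; how far its test departs from 5% rests on assumed variability. For CA125 with 58 patients the departure is slight at log-ratio SD 0.1 and material by 0.3 to 0.5. It consists almost wholly of false increase, with a loss of power for a real fall at the larger SDs. For VAS the error runs towards false worsening with few zero baselines and false improvement with many, and may cancel in between.

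The primary sign test counts directions and ranks no change rates, so this fault does not reach it, and the sample size of 58/65 stands. For cyst volume in 8.3.1 (2), no ranking of the two tests is supported.

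**What to change.** In SAP 8.3.2 (4) and 8.3.2 (5), reword the closing clause so that the test is done *for the difference; the change rate is reported with summary statistics only and is not tested*. In 8.3.2 (4) add: *Subjects with a baseline VAS of 0 have no change rate; they stay in the analysis of the difference.* This matches item 8.3.2 (3) and the general method in 7.3. Leave 8.3.1 (2) as it is.

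For CA125, a signed-rank test on log(post/pre) may be added as a sensitivity analysis; its simulated level was 4.8–5.5% for CV 10–40%.

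The cost is wording only, with no new data. Fourteen test lines go: VAS at six points (cycles 1–4, end of observation, last observation) × 2 analysis sets = 12, plus CA125 1 × 2 = 2. If VAS is not tested at cycle 1, the total is 12. These lines overlap: the two sets are nested, and SAP 6.2 defines last observation as "The last observation of the actual evaluations after cycle 1 including those at discontinuation", which for completers normally repeats the end of observation. They are not 14 separate chances of error. The downside is that the difference gives more weight to patients with high baseline values. If the finalized SAP cannot be amended, the same wording can govern how the results are reported.
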